4.1 Overall Design

We will undertake a study with 20 patients with treatment naïve biopsy proven ILC who have either: a) clinical or imaging suspicion of metastatic disease; b) biopsy proven metastatic disease but in whom there is suspicion of an even greater tumor burden that could change therapy approach. All patients will be recruited from the Winship Glenn Family Breast Cancer Program at any Emory facility. All patients will undergo Ga PSMA PET followed at minimum of 10 hours (to allow for radiotracer decay) by fluciclovine PET. (This may also happen in the opposite order, in which case 20 hours after fluciclovine will be needed to allow for decay.) There is no need for randomization since each patient will undergo both imaging techniques, and the results will be interpreted blindly. Thus, radiopharmacy scheduling will dictate the order of the radiotracers to ensure the patient will undergo both imaging modalities in the shortest time frame. Two nuclear medicine physician co-investigators, [name], will independently interpret the 20 cases, each reading half (the other reading the other half) of the fluciclovine and PSMA images (to avoid bias in always reading the same type of imaging). The readers will be blinded to all imaging including the other PET. All suspicious lesions with nonphysiologic activity above background for locoregional spread and distant disease will be identified and rated for suspicion of malignancy on a 6 point Likert scale (where 1 = definitely benign and 6 = definitely malignant). Both the primary lesion and all suspected metastases will be measured on an advanced workstation and metabolic uptake parameters (SUV, MTV, TLA) recorded. After both studies have been interpreted blindly, the third nuclear medicine physician co-investigator, [name], will blindly interpret **deidentified** PET studies on every patient (alternating for a total of 10 each fluciclovine and Ga-PSMA PET). Afterward, an unblinded reconciliation interpretation will take place with all 3 readers. To ensure balance, 10 of the studies will be reviewed for consensus first showing Ga-PSMA, then fluciclovine; 10 of the studies will be reviewed in the opposite manner. In this manner, a preliminary sense of kappa can be developed between the third and the other 2 readers, yet will guarantee the highest degree of patient care as there are currently no validated criteria for interpreting fluciclovine or PSMA PET for breast cancer. This approach will help us adapt existing prostate specific criteria to that of breast cancer. Concordant and discordant lesions between each PET study and conventional imaging will be reported and potential biopsy sites, if any, recommended. The most distant and accessible lesion may undergo biopsy in the safest manner possible (if not already done) as clinically indicated after discussion between the primary oncologist and patient.

Preference for biopsy will be given to discordant lesions. Uncommonly, in some lesions not deemed safe to biopsy, characteristic appearance on correlative imaging will be accepted as truth (e.g., MRI for certain skeletal or liver lesions). In select cases, a second biopsy of a discordant distant lesion may be required. For example, if there are 2 potentially impactful lesions which are fluciclovine positive/PSMA negative and fluciclovine negative/PSMA positive, respectively. Note that before biopsy is considered, careful scrutiny of the already obtained CT or MR will be undertaken to determine if an unsuspected anatomic correlate can be identified. This will then prompt a discussion between the patient and the referring clinician co-investigator on the benefits versus risks to definitively determine if a metastasis is present which could affect therapy. Biopsy may be undertaken in the least invasive manner as standard of care as clinically indicated, reimbursed by third party payers. Uptake parameters will be correlated with all proven primary, locoregional, and distant lesions. Verified detection rates for metastasis will be calculated for each modality.

In addition, we will collect 20 ml peripheral blood for ctDNA analysis in all patients at visit 1 (or possibly 2) to be initially processed and stored by [name] lab for off-site specialty analysis. Plasma levels of ctDNA will be measured using a targeted 28 gene panel to detect point mutations including mutations in PIK3CA, ESR1, HER2, and AKT1, genes associated with hormone therapy resistance and ILC [38, 39]. We will examine ctDNA results for association with presence or absence of locoregional metastasis on imaging as confirmed with histology, presence or absence of distant metastasis on imaging as confirmed with histology, correlation of presence or absence and absolute ctDNA with PET uptake.

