1.2 Schema

We will undertake a single arm feasibility study with n=20 patients with treatment naïve biopsy proven ILC who have either: a) clinical or imaging suspicion of metastatic disease; b) biopsy proven metastatic disease but in whom there is suspicion of an even greater tumor burden that could change therapy approach. All patients will be recruited from the Winship Glenn Family Breast Cancer Program at any Emory facility and they will have already undergone best standard of care conventional imaging (CT or MR and possibly bone scan depending on clinical presentation). **Standard of care conventional imaging typically does not include FDG PET, since FDG PET is not recommended for lobular cancer due to low sensitivity.** We will then complete both fluciclovine PET and Ga PSMA PET scans on the same patient on separate days separated by at least 10 half-lives to allow for radioactive decay. There is no need for randomization since each patient will undergo both imaging techniques, and the results will be interpreted blindly. Thus, radiopharmacy scheduling will dictate the order of the radiotracers to ensure the patient will undergo both imaging modalities in the shortest time frame. Sometimes this will mean PSMA is completed first, followed by fluciclovine, and other times the opposite. After interpretation of both studies, careful correlation to already obtained conventional imaging will then be done to determine if a previously unsuspected anatomic correlate can be identified which would impact therapy. One or two metastases (depending on scan findings) will then undergo biopsy in the safest manner possible as standard of care (if not already done) to determine the verified detection rate of metastatic disease. Uncommonly, definitive imaging such as MR for skeletal or liver lesions may be accepted in lieu of biopsy, if biopsy is not feasible. We will then compare verified detection rate of each PET study to conventional imaging and to each other. In addition, we will collect peripheral blood for ctDNA in all patients and determine if ctDNA correlates with presence or absence of metastases and tumor burden as identified by conventional imaging, fluciclovine and/or PSMA PET. Study Specific Experimental Procedures will only consist of both PET studies and ctDNA analysis. All other procedures will be conducted per standard of care. See Figure 1.

Figure 1: Trial Schema, Flow diagram

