Determine verified detection rate for metastasis of invasive lobular cancer using fluciclovine PET and PSMA PET for imaging (Specific Aims 1 and 2)

Secondary endpoints:

Correlation of ctDNA results with presence or absence of metastasis (Specific Aim 3)
Correlation of ctDNA results with results of imaging (Specific Aim 3)

4. Study Design

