5.1 Inclusion Criteria

- (Y) 1. Treatment naïve biopsy proven ILC Patients with ILC
- (Y) 2. Either: a) clinical or imaging suspicion of metastatic disease; or b) proven metastatic disease but in whom there is suspicion of an even greater tumor burden that could change therapy approach.
- (Y) 3. Ability and willingness to undergo biopsy if needed per standard of care for possible metastasis which could change therapy approach.
- (Y) 4. Age over 18

Non-English-speaking patients may be considered for enrollment in this trial. Subjects with Limited English Proficiency LEP may be enrolled and study team members will use Emory IRB approved short forms to conduct the consent process.

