Image Analysis: Two nuclear medicine physician co-investigators, [name], will independently interpret the 20 cases, each reading half (the other reading the other half) of the fluciclovine and PSMA images (to avoid bias in always reading the same type of imaging). The readers will be blinded to all imaging including the other PET. All suspicious lesions with nonphysiologic activity above background for locoregional spread and distant disease will be identified and rated for suspicion of malignancy on a 6 point Likert scale (where 1 = definitely benign and 6 = definitely malignant). Both the primary lesion and all suspected metastases will be measured on an advanced workstation and metabolic uptake parameters (SUV, MTV, TLA) recorded. After both studies have been interpreted blindly, the third nuclear medicine physician co-investigator, [name], will blindly interpret deidentified PET studies on every patient (alternating for a total of 10 each fluciclovine and PSMA PET). Afterward, an unblinded reconciliation interpretation will take place with all 3 readers. To ensure balance, 10 of the studies will be reviewed for consensus first showing Ga-PSMA, then fluciclovine; 10 of the studies will be reviewed in the opposite manner. In this manner, a preliminary sense of kappa can be developed between the third and the other 2 readers, yet will guarantee the highest degree of patient care as there are currently no validated criteria for interpreting fluciclovine or PSMA PET for breast cancer. This approach will help us adapt existing prostate specific criteria to that of breast cancer. Concordant and discordant lesions between each PET study and conventional imaging will be reported and potential biopsy sites, if any, recommended.

Correlation of histology with images: Uptake parameters as above will be correlated with all proven primary, locoregional, and distant lesions.

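### The first two PET readers are masked only to other imaging, so their ratings at sites proven before PET could be influenced by the reference result

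*Combined protocol and SAP*

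**What the plan says.** - **Initial readers.** Sections 4.1 and 9 have two nuclear medicine co-investigators read the scans, with this definition of masking: "The readers will be blinded to all imaging including the other PET". They rate each suspicious focus from 1 to 6 for malignancy. The same sections acknowledge that validated reading criteria for either tracer in breast cancer do not yet exist.
- **Third reader.** This reader "will blindly interpret deidentified PET studies on every patient", one scan per patient and ten of each tracer. Kappa is to be formed between this reader and the other two.
- **Other blinding statements.** Sections 1.2 and 4.1 say the scans are read blindly. Section 6 limits blinding to the initial read. None of them says what is withheld.
- **Entry.** Section 4.1 admits patients with "biopsy proven metastatic disease but in whom there is suspicion of an even greater tumor burden". Section 5.1 has the same route but says only that the metastasis is proven.
- **Reference standard.** Section 1.2 says that one or two metastases "will then undergo biopsy in the safest manner possible as standard of care (if not already done"), and gives determination of the verified detection rate as the purpose. Sections 1.1, 3.1, 4.1 and 8.1 also allow for a biopsy that already exists.
- **Endpoint.** The primary endpoint in Section 3.2 is: "Determine verified detection rate for metastasis of invasive lobular cancer using fluciclovine PET and PSMA PET for imaging".
- **After the initial reads.** All three readers hold an unblinded reconciliation. Section 10 does not say whether the blinded or the reconciled read enters the analysis.
- **Comparator.** Section 8.1 uses existing conventional imaging reports, up to 6 months old at enrollment, without a new read.

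**The concern.** Pathology, biopsy location, history and entry route are not imaging, so the stated masking does not cover them. A reader who follows the plan to the letter may know, before opening a scan, that a particular site is histologically positive. The reader then gives a subjective rating at a lesion whose truth is already fixed and which can count in the primary endpoint. The index test would be read with knowledge of the reference standard.

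Four results are exposed:

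- each tracer's verified detection rate;
- the sensitivity, specificity, predictive values and AUC that Section 10 derives from the Likert scores;
- the concordance between tracers in Aim 2, because knowledge of a site could push both tracers to positive there and remove a real disagreement;
- kappa, because the third reader may hold less information than the other two, and that difference would be mixed with true disagreement.

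**Working it through.** **Step 1: does another statement close the gap?** Set side by side, Sections 1.2, 4.1, 6 and 9 give one definition of what is masked (other imaging) and several uses of the word blind with no content. No section withholds pathology, biopsy sites, history or inclusion route. The gap stands.

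**Step 2: does it reach the primary endpoint?** Entry with a biopsy-proven metastasis is allowed, and an existing biopsy can supply verification. Known sites can therefore be among the lesions that count.

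**Step 3: the plan's own figures.** Section 10 gives no power for the 20 patients. It gives McNemar sample sizes for a later trial. An exact one-sided McNemar test at 0.05 with 80% power reproduces all seven: 67, 83, 99, 118, 175, 42 and 63. Masking does not change them, and none of them measures this effect.

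**Step 4: an illustration of size.** Section 10 counts sample size in patients, so the patient is used as the unit here.

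- N = 20 (Section 10).
- Share with a site documented before PET: not given. Proxy: 37% Stage 4 at presentation (Section 5). 0.37 × 20 = 7.4, about 7 patients.
- Gain in the PET-positive rate at a known site from knowing it: assumed, 10 to 30 points.

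Extra detections = 7 × gain:

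- 10 points: 7 × 0.10 = 0.7 patients; 0.7 / 20 = 3.5 points.
- 30 points: 7 × 0.30 = 2.1 patients; 2.1 / 20 = 10.5 points.

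For a given gain this is a ceiling. It treats every Stage 4 patient as biopsied before PET. It also assumes that no such patient has another verified PET-positive lesion, which would leave the patient-level result unchanged.

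**Step 5: a wider range.** Inflation = k × (1 − s) × g, where k is the share with a known site, s is PET sensitivity there without the information, and g is the share of misses turned positive. All three are assumptions.

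| k | s | g | points | patients of 20 |
|---|---|---|---|---|
| 0.20 | 0.8 | 0.25 | 1.0 | 0.2 |
| 0.37 | 0.8 | 0.50 | 3.7 | 0.74 |
| 0.37 | 0.6 | 0.50 | 7.4 | 1.48 |
| 0.37 | 0.6 | 1.00 | 14.8 | 2.96 |
| 0.50 | 0.6 | 1.00 | 20.0 | 4.0 |

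The spread of 1 to 20 points shows how little the documents fix the size.

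**Step 6: scale.** The Clopper-Pearson 95% interval is 36.1 to 80.9% for 12/20 and 45.7 to 88.1% for 14/20. Sampling error is larger than the likely effect, but the interval makes no allowance for a bias with a direction.

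**The case against.** The strongest reply is that this is silence, not a stated practice. A reader might infer that the first two readers will be given pathology, or that their scans carry patient identity. The documents say neither. They say that the scans are read blindly, and they use the word deidentified only for the third reader. That word may not be a blinding measure at all: Section 13 restricts an outside collaborator to deidentified images for ethics-review reasons, and the third reader could be that person. The documents do not settle this, so the contrast between readers shows unequal stated conditions, not proven unequal knowledge.

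A reader might also infer that PET is favoured over conventional imaging because the latter was reported before biopsy. Section 8.1 does not establish that order. The comparator reports are clinical and are not stated to be blinded. A previously biopsied site may also have been chosen because conventional imaging showed it. The net bias in that comparison is therefore uncertain.

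Two further limits stand. Knowing a site does not create uptake, so only equivocal foci are open to influence. Nor can it help at previously unsuspected lesions, which are the focus of Aim 1. It is also fair that a 20-patient exploratory study with wide intervals will not turn on one or two patients.

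What remains is that the only definition of masking leaves out the reference result, on a subjective scale, for lesions that can count in the primary endpoint.

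**Conclusion.** The gap is real and worth closing. It is a risk that the plan leaves open, not a demonstrated bias. Ratings at sites proven before PET could be influenced by the reference result. That could raise both PET detection rates and the Likert scores there, conceal disagreement between tracers, and blur kappa. Under the Stage 4 proxy and an assumed gain of 10 to 30 points, the effect is at most about 0.7 to 2.1 of 20 patients (4 to 11 points). Both the proxy and the gain are assumptions, so this is not an estimate. It does not extend to newly found sites.

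It would be wrong to set this range against the 15 to 25 point differences in Section 10. Those are paired differences between modalities for a later trial, whereas this is possible inflation of a single modality's rate.

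The unblinded reconciliation matters as well. If its result is the one analysed, masking the initial reads would not protect the endpoint.

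**What to change.** 1. In Sections 4.1 and 9, state that all initial reads use deidentified scans, and that all three readers are masked to pathology, biopsy sites, clinical history and inclusion route until their scores are locked. Deidentification alone is not enough, so the withheld items should be named.
2. In Section 10, state that the locked blinded reads, not the unblinded reconciliation, feed the verified detection rates, the Likert-based accuracy measures and kappa.
3. Release clinical information at the reconciliation, before potential biopsy sites are recommended.
4. Optionally, report sites proven before PET separately from newly found sites.

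The cost is a few sentences and no added reader or read. There are 20 × 2 = 40 scans, and the third reader's 10 + 10 = 20 are already to be deidentified, so about 20 more need it. All must be prepared before the first read. The one downside is that the first read lacks clinical history, which is restored at reconciliation.

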Specific Aim 1: Improve detection of metastasis with fluciclovine and PSMA PET versus best standard of care conventional imaging, as confirmed with histology. We will image 20 patients with ILC who have either: a) clinical or imaging suspicion of metastatic disease; or b) proven metastatic disease but in whom there is suspicion of an even greater tumor burden that could change therapy approach. Abnormal foci which correlate to anatomic lesions previously unsuspected on conventional imaging will undergo optional biopsy as clinically indicated in the safest manner possible (if not already done) to determine the verified detection rate of metastatic disease.

Specific Aim 2: Determine concordance and discordance of ILC detection with PSMA versus fluciclovine PET, as confirmed with histology. We will compare verified detection rates for metastasis between fluciclovine and PSMA PET modalities. This may necessitate a second biopsy of a

[figure not shown]
distant lesion discordant between the 2 PET techniques. We will also analyze images for biodistribution in the primary lesion(s) for both radiotracers.

Exploratory Aim 3: Establish the role of molecular detection by ctDNA mutations including PIK3CA, ESR1, HER2, and AKT1 in characterizing the degree of tumor burden as identified by metabolic amino acid transport and/or tumor neovasculature receptor imaging [12]. We will collect peripheral blood for ctDNA in all patients and determine if ctDNA correlates with presence or absence of metastases and tumor burden as identified by fluciclovine (metabolic) and/or PSMA (angiogenesis) PET.

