2) MR: If a lesion is not deemed safe or possible to biopsy, MR may then be performed (e.g. for bone or liver). MR, even with the administration of Gadolinium is considered a safe and effective noninvasive imaging procedure. In addition to the small possible reactions to contrast material if used, claustrophobia while in the magnet is a potential risk, as well as reaction from metal within the body. Yet at Emory, special screening is performed before MR to determine if the patient has tattoos or any metal items in the body such as implants, pacemakers, clips or shrapnel, to make sure the MRI scan is done safely.

3. Objectives and Endpoints

3.1 Study Objectives:

Our major goal in this proposed investigation is to use advanced molecular imaging to better detect metastases in patients with invasive lobular cancer.

Specific Aim 1: Improve detection of metastasis with fluciclovine and Ga-PSMA PET versus best standard of care conventional imaging, as confirmed with histology. We will image 20 patients with ILC who have either: a) clinical or imaging suspicion of metastatic disease; or b) proven metastatic disease but in whom there is suspicion of an even greater tumor burden that could change therapy approach. Abnormal foci which correlate to anatomic lesions previously unsuspected on conventional imaging will undergo optional biopsy as clinically indicated in the safest manner possible (if not already done) to determine the verified detection rate of metastatic disease.

Specific Aim 2: Determine concordance and discordance of ILC detection with Ga-PSMA versus fluciclovine PET, as confirmed with histology. We will compare verified detection rates for metastasis between fluciclovine and PSMA PET modalities. This may necessitate a second biopsy of a distant lesion discordant between the 2 PET techniques. We will also analyze images for biodistribution in the primary lesion(s) for both radiotracers.

Exploratory Aim 3: Establish the role of molecular detection by ctDNA mutations including PIK3CA, ESR1, HER2, and AKT1 in characterizing the degree of tumor burden as identified by metabolic amino acid transport and/or tumor neovasculature receptor imaging [12]. We will collect peripheral blood for ctDNA in all patients and determine if ctDNA correlates with presence or absence of metastases and tumor burden as identified by fluciclovine (metabolic) and/or PSMA (angiogenesis) PET.

3.2 Study Endpoints:

Primary endpoint:

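### Aim 2 concordance is to be histology-confirmed, but biopsy favours discordant lesions and Section 10 sets no unit, no denominator and almost no rule for unverified lesions

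*Combined protocol and SAP*

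**What the plan says.** The primary endpoint (Section 3.2) is a verified detection rate for each tracer. Section 3.1 and Section 10 tie the Aim 2 concordance and discordance results to histological confirmation.

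**Who is verified.** Aim 1 (Sections 1.1 and 3.1) states: "Abnormal foci which correlate to anatomic lesions previously unsuspected on conventional imaging will undergo optional biopsy as clinically indicated". Section 1.2 foresees biopsy of one or two metastases. Section 4.1 adds "The most distant and accessible lesion may undergo biopsy in the safest manner possible (if not already done) as clinically indicated", then "Preference for biopsy will be given to discordant lesions"; Section 8.1 repeats the preference. Aim 2 in Section 3.1 says of a further biopsy: "This may necessitate a second biopsy of a distant lesion discordant between the 2 PET techniques".

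**What discordant means.** Just before the preference, Section 4.1 says "Concordant and discordant lesions between each PET study and conventional imaging will be reported". Its example for a second biopsy is instead between tracers: "For example, if there are 2 potentially impactful lesions which are fluciclovine positive/PSMA negative and fluciclovine negative/PSMA positive, respectively".

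**Lesions without biopsy.** Sections 1.2, 4.1 and 8.1 accept a characteristic appearance on other imaging for some lesions that cannot safely or feasibly be biopsied; Sections 1.2 and 4.1 call this uncommon. Sections 1.3 and 4.4 provide medical-record follow-up for up to 5 years, with no rule for turning it into lesion status.

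**Reads and analysis.** Lesions are "rated for suspicion of malignancy on a 6 point Likert scale (where 1 = definitely benign and 6 = definitely malignant"), with no cut-off for a positive read. Section 10 names McNemar's test, Clopper-Pearson intervals for each method's own rate, and rates of concordant and discordant observations. It does not say whether an observation is a patient or a lesion. It then sizes a later study, in patients, from a discordant rate and a difference in detection.

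**The concern.** Whether a lesion is verified may depend on the very thing Aim 2 measures. If lesions on which the tracers disagree are biopsied first, and concordance is then computed among lesions with histology, disagreement is over-represented. This is partial verification.

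The plan leaves open the choices that decide whether this happens: which sense of discordant applies, patient or lesion as the unit, the denominator, and the status of unverified lesions. The same scans can then give very different results, and the denominator could be chosen after the data are seen.

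Section 10 says the pilot's purpose is to estimate effect size for a larger study. The two quantities exposed here, the discordant rate and the paired difference, are exactly the inputs to its sample-size list. The difference itself is given no interval.

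**Working it through.** **1. Reproduce the plan's sizes.** Unconditional power of the exact McNemar test, summed over the number of discordant pairs; smallest N with power of at least 80%; one-sided 0.05. For discordance/difference:
- 40/20, 50/20, 60/20: 67, 83, 99
- 40/15, 60/15: 118, 175
- 40/25, 60/25: 42, 63

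All seven match Section 10. The section does not state sidedness; two-sided exact gives 84, 103 and 124 for the 20-point row.

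**2. Denominator alone.** Suppose 12 verified detections (assumed). With Clopper-Pearson 95% intervals:
- of 20 enrolled: 60% (36 to 81)
- of 18 after the 10% dropout expected in Section 5: 67% (41 to 87)
- of 15 biopsied (assumed): 80% (52 to 96)

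**3. Selective verification: illustration only.** Assumed, not in the documents: every lesion is a true metastasis, sensitivities are 80% (fluciclovine) and 60% (PSMA), detections are independent, there are three lesions per patient and one biopsy, and the preference is PET versus PET.

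Per lesion: fluciclovine only 0.8 × 0.4 = 0.32; PSMA only 0.2 × 0.6 = 0.12; both 0.48; neither 0.08. So discordant = 0.44 and seen on either PET = 0.92.
- All lesions seen: 0.44/0.92 = 0.478; difference 0.20/0.92 = 0.217.
- Biopsied lesions, preference always followed: (1 − 0.56³)/(1 − 0.08³) = 0.8244/0.9995 = 0.825; difference 0.825 × 0.20/0.44 = 0.375.
- Biopsied lesions, preference followed in half of patients: (0.478 + 0.825)/2 = 0.652; difference 0.652 × 0.20/0.44 = 0.296.
- All lesions seen, unverified counted as not detected: multiply the two biopsied-lesion results by (1 − 0.08³)/(3 × 0.92) = 0.362, giving 0.236 to 0.299; difference 0.107 to 0.136.
- Patient level, any lesion seen, reads only: (0.4³ − 0.08³) + (0.2³ − 0.08³) = 0.071; difference 0.4³ − 0.2³ = 0.056.

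With one lesion per patient there is no bias among biopsied lesions. A separate simulation with partly correlated detections and a second biopsy when both discordant types are present gave 37% among lesions seen and 71% among biopsied ones, at three lesions per patient.

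**4. Carry to the next study's size.** By the method of step 1, counting independent pairs:

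| Basis | Discordance | Difference | N |
|---|---|---|---|
| All lesions seen | 47.8% | 21.7 points | 67 |
| Biopsied, half preference | 65.2% | 29.6 points | 49 |
| Biopsied, full preference | 82.5% | 37.5 points | 39 |
| All seen, unverified as not detected | 23.6–29.9% | 10.7–13.6 points | 136–108 |

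Among biopsied lesions both inputs rise together and N falls. Under the last convention N rises.

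**5. Precision of a paired difference.** Tango 95% intervals: 6 versus 2 discordant patients of 20 gives 20.0 points (−8.6 to +45.7); 5 versus 2 of 18 gives 16.7 points (−13.4 to +44.0). The counts are assumed. A wide interval is itself information for planning.

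**The case against.** The best defence has four parts.

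First, a reader might infer that the plan has no rule at all for unbiopsied lesions. That is too strong: the imaging exception is a rule, and later histology and imaging are collected in follow-up. But the exception is narrow, and follow-up has no rule for deciding lesion status.

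Second, the preference follows directly on the PET-versus-conventional wording, so that may be its intended sense. The between-tracer sense appears only for a second biopsy in select cases. Accessibility, clinical indication and existing biopsies also limit the preference. This stands: neither the existence of the bias in Aim 2 nor its strength is certain. It is also the reason the sense must be stated.

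Third, McNemar's p-value uses only discordant pairs, so at lesion level it need not be distorted if both discordant types are verified equally often. That is correct, but it does not protect the rates, the difference or the discordant rate, and nothing ensures equal verification.

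Fourth, this is a 20-patient exploratory study with no power analysis, and sizing the later study in patients hints at a patient-level unit. But the later sizing depends on these estimates, and patient-level detection is not defined for this study.

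A reader might also take the list's move from 67 to 99, as discordance goes from 40% to 60%, as the consequence. The documents do not support that: the list holds the difference at 20 points, whereas selective biopsy moves both inputs. Nor does dropout alone turn 67 into 74. That result needs all dropout to fall before biopsy, dropouts to count as not detected (36% discordance, 18 points), and a one-sided test.

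**Conclusion.** The concern holds in a conditional form. What is certain from the text is that confirmation is optional and selective, that Section 10 fixes neither unit nor denominator, that most unverified lesions have no stated treatment, and that the paired difference has no interval.

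Upward bias in the discordant rate follows if three conditions hold together: the PET-versus-PET sense, several lesions per patient, and rates taken among verified lesions. The difference may then be distorted too. Otherwise the bias may be absent or reversed.

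The size rests wholly on the assumed inputs. In the illustration, a later study planned from biopsied-lesion rates would be 18 to 28 pairs short (67 − 49, 67 − 39) if it analysed all lesions. That later study's design is not in the documents, so no actual loss of power can be claimed. This should be corrected before results are known; it is not a safety matter.

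**What to change.** Change Section 10 only; biopsy practice stays as it is.

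1. State which sense of discordant applies. Make the patient the primary unit for McNemar's test, with all patients who complete both PETs as the denominator. State the Likert cut-off for a positive read and a truth rule (histology, accepted imaging, or follow-up by a stated definition). Report patients without verification separately and in best-case and worst-case sensitivity analyses. Make lesion level secondary and clustered by patient.
2. Report PET-versus-PET concordance from the initial blinded reads over all recorded lesions, labelled unverified. Beside it give histology results by read pattern (both positive, fluciclovine only, PSMA only) as confirmed / biopsied / seen, labelled selectively verified.
3. Give a 95% paired interval for the patient-level difference (for example Tango) and a patient-cluster interval at lesion level (for example a bootstrap by patient).
4. Do not size the next study from raw biopsied-lesion rates unless it uses the same unit and verification rule.

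Cost: mostly wording, because lesions are already recorded and rated at the blinded reads. Matching lesions across the two PETs is extra work and needs a short rule. All-read concordance may include false positives: with an assumed 0.10 false-positive foci per true lesion on each tracer, the illustrative 48% becomes (0.44 + 0.20)/(0.92 + 0.20) = 57%. It may also include reader differences, since the two readers split the images, "each reading half (the other reading the other half) of the fluciclovine and PSMA images". Patient-level discordance can be near zero when patients have many lesions (7% in the illustration), so the lesion table is still needed.
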